6.9.5 Physical Examination

Results from physical examinations will be listed by participant at each visit.

6.10 Analysis of Pharmacokinetic Data

A descriptive summary of serum concentration data will be presented. Serum concentration will be listed for each participant by visit.

Following figures will be provided for the serum concentration data,

- Mean ($\pm SD$) serum concentration vs time profile: Linear scale
- Mean ($\pm SD$) serum concentration vs time profile: Semi-log scale
- Individual serum concentrations vs time profile: Linear scale

- Individual serum concentrations vs time profile: Semi-log scale

6.11 Analysis of Pharmacodynamic Data

Pharmacodynamic data (including data from biopsies) will be made available during the time of clinical database lock. Descriptive statistics of the following variables will be presented.

- Listing of TARC concentration by visit
- Summary of TARC concentration change from baseline over time
- Listing of RO by visit
- Summary of RO change from baseline over time
- Listing of OX40+/CD4+ percentage by visit
- Summary of OX40+/CD4+ percentage change from baseline over time
- Listing of Percentage of K16-positive cells in the epidermis by visit
- Summary of Percentage of K16-positive cells in the epidermis change from baseline over time
- Listing of the number of OX40 positive cells by visit
- Summary of the number of OX40 positive cells change from baseline over time
- Listing of the number of OX40L positive cells by visit
- Summary of the number of OX40L positive cells change from baseline over time
- Listing of skin thickness by visit
- Summary of skin thickness change from baseline over time
- Summary of eosinophil change from baseline over time

6.12 Analysis of Immunogenicity Data

The ADA variables will be summarized using descriptive statistics in the immunogenicity analysis set. Frequency tables of the proportion of participants developing ADA positivity in the ADA assay, pre-existing ADA, treatment-emergent, treatment-boosted, persistent, indeterminate and transient ADA responses will be presented as absolute occurrence (n) and percent of participants (%).

Listing of ADA data will be provided.

The following summaries will be performed on the immunogenicity analysis set:

- Number (%) of patients negative ADA at all the time points analyzed
- Number (%) of patients ADA positive at time points analyzed
- Number (%) of patients with pre-existing ADA, treatment-emergent ADA, and treatment boosted ADA response
- Number (%) of patients with persistent, transient and indeterminate treatment-emergent ADA response
- Descriptive statistics of PK concentration in ADA positive and ADA negative participants.

7. DATA CONVENTIONS

The following analysis conventions will be used in the statistical analysis.

7.1 Definition of Baseline for Efficacy/Safety Variables

Unless otherwise specified, the baseline assessment for all measurements will be the latest available valid measurement taken prior to the administration of study drug (Week 0 (Day 1)). When it is not possible to determine the time of assessment, baseline value would be determined based on the measurement recorded on the day administration of the first dose of IMP.

7.2 Data Handling Convention Missing Data

Missing data will not be imputed in listings. This section includes the methods for missing data imputation for some summary analyses, if necessary.

Adverse event

If the intensity of a TEAE is missing, it will be classified as “severe” in the frequency tables by intensity of TEAE. If the assessment of relationship of a TEAE to the investigational product is missing, it will be classified as “related” in the frequency tables by relation to the investigational product.

The partial date values will be imputed as specified in the [Appendix 12.2](#). Imputed dates will not be presented in the listings.

[figure not shown]
7.3 Analysis Visit Window

[figure not shown]
For summaries that include data collected over multiple visits, where appropriate, the data will be summarized by analysis visit window. If there are multiple measurements within a scheduled visit window (refer [Appendix 12.6](#)), the closest measurement to the scheduled timepoint of the visit will be used in the analysis. If there are two observations which have the same difference in days to the planned day, but which are not measured on the same day, the later value will be selected. If there is more than one observation on the same day then;

- Latest value will be considered in all cases except for vital signs, ECG.
- Average value will be considered in cases of continuous vital signs and ECG parameters.
- The worst value will be considered for ECG interpretation.

All measurements will be presented in the listing.

[figure not shown]

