7.5 Pharmacodynamics Assessments

7.5.1 Circulating Biomarkers

Blood samples will be sampled for biomarker analysis.

Blood samples for analysis of receptor occupancy (RO) will be collected at Baseline (Day 1, pre-dose and end of infusion [EOI]), Week 1 (Day 8), Week 2 (Day 15, pre-dose and EOI), Week 4 (Day 29, pre-dose and EOI), Week 6 (Day 43), Week 8 (Day 57), Week 12 (Day 85)/EOT, Week 16 (Day 113), Week 20 (Day 141), and Week 24 (Day 169)/EOS.

Blood samples for analysis of inflammatory markers including TARC will be collected at Baseline (Day 1, pre-dose), Week 1 (Day 8), Week 2 (Day 15, pre-dose), Week 4 (Day 29, pre-dose), Week 6 (Day 43), Week 8 (Day 57), Week 12 (Day 85)/EOT, Week 16 (Day 113), Week 20 (Day 141), and Week 24 (Day 169)/EOS.

The sampling window for PD assessments of RO and inflammatory markers are as defined in [Table 5](#). Details concerning the handling of blood samples, including labeling and shipping instructions are provided in the Laboratory Manual.

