4.7 Pharmacokinetic (PK) Variables

The blood samples will be collected at day 1/baseline (pre-dose and EOI), days 8, 15 (pre-dose and EOI), 29 (pre-dose and EOI), 43, 57, 85/EOT, 113, 141, and 169/EOS to describe IMG-007 concentration profiles at specified visit.

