12.6 Analysis Visit Window

Analysis Visit	Target Day	Group 1	Group 2	Group 3*	Group 4	Group 5	Group 6
Baseline	1	Up to day 1	-	Up to day 1			
Week 1	8	2-11	2-11	-	-	-	-
Week 2	15	12-22	12-22	2-22	2-22	-	2-22
Week 4	29	23-36	23-36	23-57	23-43	2-43	23-43
Week 6	43	37-50	37-50	-	-	-	-
Week 8	57	51-64	51-64	-	44-64	44-64	44-64
Week 12	85	65-92	65-92	58-127	65-92	65-92	65-92
Week 16	113	93-120	93-120	-	93-120	93-120	93-120
Week 20	141	121-148	121-148	-	121-148	121-148	121-148
Week 24	169	149-172	149-172	128-172	149-172	149-172	149-172

Group 1: Vital signs, Physical examination, Adverse events, Prior and concomitant therapies, Hematology, blood chemistry, EASI, IGA, SCORA, Itch and sleep quality NRS, PGIS, PK sampling, Receptor occupancy and TARC.

Group 2: PGIC

Group 3: Urinalysis

Group 4: Pregnancy test

Group 5: DLQI.

Group 6: ADA sampling

*Use group 3 for ECG and TB assessment by removing week 2 and week 4 and changing the Week 12 window from '58-127' to "2-127".

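### As written, SAP 7.3's same-day rule puts end-of-infusion rather than pre-dose PK and receptor-occupancy values into the Week 2 and Week 4 summaries, and its averaging of vital signs conflicts with SAP 6.9.3

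*SAP*

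**What the plan says.** SAP 7.3 assigns data to analysis visit windows and then resolves multiple values. The value nearest the scheduled time is used first. For several observations on the same day the rule is "Latest value will be considered in all cases except for vital signs, ECG", and for the exceptions "Average value will be considered in cases of continuous vital signs and ECG parameters". All measurements are still listed.

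Appendix 12.6 applies the windows by data type. Group 1 begins "Group 1: Vital signs, Physical examination, Adverse events" and ends "PK sampling, Receptor occupancy and TARC". Each visit has one target day and one day range; no clock time or nominal timepoint appears.

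The sampling plan has two samples on each dosing day. For PK, SAP 4.7 lists Day 1 pre-dose and EOI, Day 8, then "15 (pre-dose and EOI), 29 (pre-dose and EOI), 43, 57, 85/EOT, 113, 141, and 169/EOS". For RO, Protocol 7.5.1 has the same pattern, including "Week 2 (Day 15, pre-dose and EOI), Week 4 (Day 29, pre-dose and EOI". The inflammatory markers, including TARC, are pre-dose only on dosing days.

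The analysis sections do not separate the two. SAP 6.10 says "A descriptive summary of serum concentration data will be presented"; SAP 6.11 plans RO change from baseline over time. Baseline under SAP 7.1 is the "latest available valid measurement taken prior to the administration of study drug".

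For vital signs, SAP 4.6.3 plans four readings per dosing day: before infusion, 15 minutes after its start, 15 minutes after EOI and 1 hour after EOI. SAP 6.9.3 asks for both descriptive statistics and notable findings at visit/timepoint level.

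**The concern.** A rule for choosing among same-day values normally handles accidental repeats. Here it is stated for all cases, and the planned pre-dose and EOI samples are themselves same-day values. A programmer who follows the text would treat two deliberate timepoints as duplicates and keep the later one.

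The pre-dose samples on Days 15 and 29 are each taken two weeks after the preceding infusion, as is the Day 43 sample. Together they form a like-for-like series. Replacing the first two with post-infusion values breaks it, and RO change from baseline would compare a pre-dose baseline with post-infusion values at just those two visits. SAP 1.2.2 lists PK characterisation as a secondary objective (the protocol lists it as exploratory). Cohort 1 is now the only cohort, and the protocol expects it to inform a Phase 2b design.

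For vital signs, one average per dosing day cannot populate a table by timepoint, so the two SAP sections cannot both be followed literally.

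**Working it through.** The plan states no figure to reproduce; the check applies its rule to its own schedule.

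**1. Which sample is selected.** The Week 2 window is Days 12 to 22 and the Week 4 window Days 23 to 36 (Appendix 12.6). The pre-dose and EOI samples share a calendar day, so they are equally far from a target expressed in days. The same-day rule then applies, and the later sample is EOI. PK and RO are not among the exceptions.

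**2. Day 1.** The Baseline window runs up to Day 1, so the Day 1 EOI sample falls inside it. SAP 7.1 bars it from being the baseline value, and the Week 1 window starts at Day 2. It therefore has no row in a by-visit summary.

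**3. Count, per assay.** Scheduled samples: Day 1 pre-dose and EOI, Day 8, Day 15 pre-dose and EOI, Day 29 pre-dose and EOI, and Days 43, 57, 85, 113, 141 and 169, which is 13 per participant.
- 13 samples × 13 enrolled participants = 169.
- Displaced by the same-day rule: 2 × 13 = 26, and 26/169 = 15.4%.
- Day 1 EOI without a by-visit row: a further 13.
- Post-baseline visits: 9, of which 2 (Weeks 2 and 4) would hold EOI values and 7 off-dose values.

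**4. Size for concentration (illustration).** Assumptions: one compartment, bolus-like input, three equal doses 14 days apart. The 31-day mean terminal half-life is from Protocol 2.2 (healthy participants, 300-600 mg); the 20 to 40 day range is assumed. In units of the single-dose peak, with r = exp(−ln 2 × 14 / half-life):
- Day 15: pre-dose r, EOI 1 + r, ratio (1 + r)/r.
- Day 29: pre-dose r + r², EOI 1 + r + r², ratio (1 + r + r²)/(r + r²).
- Day 43: r × (Day 29 EOI).

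| Half-life | r | Day 15 pre → EOI (ratio) | Day 29 pre → EOI (ratio) | Day 43 |
|---|---|---|---|---|
| 20 d | 0.616 | 0.616 → 1.616 (2.62) | 0.995 → 1.995 (2.01) | 1.228 |
| 31 d | 0.731 | 0.731 → 1.731 (2.37) | 1.266 → 2.266 (1.79) | 1.657 |
| 40 d | 0.785 | 0.785 → 1.785 (2.27) | 1.400 → 2.400 (1.71) | 1.883 |

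The selection also reverses the direction from Week 4 to Week 6. At 31 days the pre-dose series rises from 1.27 to 1.66, whereas the literal rule shows a fall from 2.27 to 1.66. No comparable figure can be given for RO.

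**5. Vital signs.** On Days 15 and 29, 13 × 2 × 4 = 104 planned readings per parameter would become 13 × 2 = 26 averages. A change in one of four readings is divided by four: 30 mmHg becomes 7.5 mmHg. For the criterion of temperature above 39.0, with the other three readings at a (assumed), one reading must exceed 4 × 39.0 − 3a = 156 − 3a for the average to be flagged:
- a = 36.5: 46.5
- a = 37.0: 45.0
- a = 37.5: 43.5
- a = 38.8: 39.6

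So 40.0 with three readings of 37.0 averages 37.75 and is missed, while 39.8 with three of 38.8 averages 39.05 and is flagged.

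**The case against.** The strongest reply is that the rule was meant for true repeats. SAP 7.3 applies windows only where that is suitable, and its first criterion speaks of a scheduled timepoint, which could mean pre-dose or EOI. SAP 6.10 plans concentration-time profiles without mentioning windows. Protocol 11.3.5 lists biomarker data by visit and timepoint, exposure-efficacy work goes to a separate population PK/PD plan, and the mock shells cited in SAP 6 are not available here. This makes the intended reading plausible and leaves the plots not necessarily affected. It does not change the text: Appendix 12.6 names PK and RO and sets targets in days only, the Protocol 11.3.5 wording concerns listings, and Protocol 11.3.2 summarises PK for each visit.

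For vital signs the reply is stronger. SAP 6.9.3 is the specific section, already requires timepoint-level summaries, and most naturally overrides a general convention. What remains is a conflict that SAP 7.3 leaves unacknowledged.

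Two stronger inferences are tempting. One is that averaging would hide every isolated threshold crossing. Step 5 shows that this depends on the other readings, and SAP 6.9.3 probably rules such averaging out. The other, since notable vital-sign findings are in the Safety Review Committee package (SAP 9.2), is that live infusion monitoring was weakened. The documents do not support it. Enrolment ended on 31 January 2024; if Day 1 was that date, Day 29 was 28 February, and the maximum 10-day delay gives 9 March, before SAP version 2.0 of 17 May 2024. Clinically significant vital signs must also be reported as adverse events (Protocol 8.2.3.1).

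**Conclusion.** The point holds for PK and RO: a stated rule, followed literally, gives the wrong by-visit summary at two of nine post-baseline visits, and no other section of the SAP overrides it. The size is 26 of 169 scheduled samples per assay, assuming complete sampling of 13 participants. EOI/pre-dose concentration ratios are about 2.4 and 1.8 under the illustrative model (2.6 to 2.3 and 2.0 to 1.7 over half-lives of 20 to 40 days). The Day 1 EOI sample is inside the Baseline window but has no usable row.

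For vital signs the finding is narrower: SAP 7.3 and 6.9.3 conflict and need reconciling, with 6.9.3 the likely governing text.

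The effect is confined to descriptive PK, RO and vital-sign summaries. TEAE incidence, EASI, TARC, the pre-dose baseline and the listings are unaffected. Whether the error would reach the tables depends on how the programmers read the rule, which the SAP should not leave open.

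**What to change.** - SAP 7.3: state that the window and same-day rules (latest, average) operate within a nominal timepoint, so that they resolve true repeats only.
- SAP 6.10 and 6.11: state that PK and RO are summarised separately at pre-dose and EOI on dosing days, including Day 1 EOI.
- SAP 7.3: add a cross-reference that SAP 6.9.3 governs vital signs, with descriptive statistics and notable findings by timepoint.

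The cost is a sentence in each place, a nominal-timepoint key in the PK, RO and vital-sign programs, and more table rows. No new data are needed. If tables have already been produced, the same wording serves as a check on which sample was used at Weeks 2 and 4.

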8. INTERIM ANALYSIS

[figure not shown]

All analysis in which inferential statistics will be generated will be interpreted using the two-sided nominal alpha of 0.05.

8.1 Interim Efficacy Analyses

8.2 Interim Safety Analyses

[REDACTED]

[REDACTED]

[REDACTED]

[REDACTED]

[REDACTED]

9. SAFETY REVIEW COMMITTEE

A safety review committee (SRC) consisting of three independent physicians will be convened to review safety data, dose escalation criteria, and the study stopping criteria. A SRC will be convened to review safety data and the study stopping criteria.

9.1 SRC Efficacy Analyses

Efficacy data to be presented in the SRCs will include the following:

- Mean and mean % change from baseline in EASI by visit

9.2 SRC Safety Analyses

Safety data to be presented in the SRCs will include the following:

TEAE

- Overall summary of TEAE
- Summary of TEAEs by SOC and PT
- Summary of Serious TEAEs by SOC and PT
- Summary of TEAEs with CTCAE grade 3 or higher by PT
- Summary of treatment related TEAEs by SOC and PT

Lab values

- Number (n) and percentage (%) of participants with CTCAE grade for key hematology parameters (WBC, neutrophils, lymphocytes, eosinophils, platelet, and hemoglobin)
- Number (n) and percentage (%) of participants with CTCAE grade for key serum chemistry parameters (ALT, AST, serum creatinine, and bilirubin)

Vital signs

- Notable findings in vital signs

ECG

- Notable findings in ECG

10. SOFTWARE

All analyses will be done using SAS Version 9.4 or above.

12. APPENDIX

12.1 Schedule of Assessments

Procedures	Screening	Treatment Period							Follow-up Period		
		Baseline						EOT ¹³			EOS ¹³
Visit	V1	V2	V3	V4	V5	V6	V7	V8	V9	V10	V11
		Week 0	Week 1	Week 2	Week 4	Week 6	Week 8	Week 12	Week 16	Week 20	Week 24
		Day -35 to -1	Day 1	Day 8	Day 15	Day 29	Day 43	Day 57	Day 85	Day 113	Day 141
Time window			± 3d	± 3d	± 3d	± 3d					
DLQI ¹²			X			X		X	X	X	X
AD lesion photograph (optional)			X						X		X
PK sampling			X	X	X	X	X	X	X	X	X
ADA sampling			X		X	X	X	X	X	X	X
Receptor occupancy and TARC			X	X	X	X	X	X	X	X	X
Skin biopsy (optional)			X						X		X

1. Study-specific procedures will be performed after receipt of signed informed consent.
2. Medical history includes prior/concurrent relevant conditions and medications, prior/current AD treatment, and surgical history. At the Baseline visit, medical history is updated prior to administration of study treatment.
Demographics include date of birth, gender, race and ethnicity, height, and body weight. BMI will be calculated as weight (kg) / [height (m) x height (m)].
3. Vital signs include respiratory rate, blood pressure, pulse, and body temperature. On study treatment dosing days, i.e., Baseline (Day 1), Week 2 (Day 15), and Week 4 (Day 29), vital signs should be assessed 15 (± 5) minutes before initiation of infusion; 15 (± 5) minutes after the initiation of the infusion; 15 (± 5) minutes after EOI, and 1 hour (± 15 minutes) post EOI. Participants need to rest for 5 minutes before having their vital signs measured.
4. Physical examination: A full physical examination will be performed at Screening. A brief physical examination will be completed at the Baseline visit, and symptom-directed physical examinations will be completed at each follow-up visit at the discretion of the investigator.
5. Laboratory assessments will be analyzed at a central laboratory. If lab test results do not meet the inclusion/exclusion criteria at Screening, a repeat test may be performed.
6. All participants will undergo TB test (Quantiferon-TB Gold [QFT-G] test or an equivalent test) at a central or local laboratory at Screening. Participants who receive study treatment will be followed up by a TB risk assessment questionnaire (see [Appendix 1](#)) at Week 12 and Week 24/EOS. If the participants have a negative TB test at the initial screening evaluation, the TB test could be waived at the rescreening if no changes in the participant's medical history that warrant retesting, and no more than 90 days have passed.
7. Viral disease screening includes HBsAg, HBsAb, HBcAb, HCV antibody and HIV antibody. Participants who do not complete the viral disease screening test before the execution of V3.0 protocol should request testing at one of the subsequent visits through a central or local laboratory as feasible.
8. Pregnancy tests are only for women who are of childbearing potential. Serum hCG will be performed at the Screening, Baseline (Day 1), Week 1 (Day 8), Week 2 (Day 15), Week 4 (Day 29), and at the selected follow-up visits. In addition, a urine pregnancy test must be performed prior to dosing on Baseline (Day 1), Week 2 (Day 15), and Week 4 (Day 29), which will be conducted at the study site.
9. On dosing days, study treatment will be administered as an IV infusion over approximately 60 minutes with a slower rate during the first 15 minutes. Participants will be closely monitored at the study site for a minimum of 1 hour after completion of each infusion or until any AEs observed have resolved or stabilized, whichever is longer. For diagnostic purposes, any participant who experiences any systemic infusion-related event should have a blood sample taken ideally 30–60 minutes after the onset for tryptase testing and samples may be analyzed

by a central or local laboratory. Study sites should have access to equipment or facilities for the management of potential hypersensitivity reactions. On dosing days, study treatment infusion should be performed after other study assessments have been performed. The study site will contact participants by telephone approximately 24 hours after the infusion for general AE query.

10. EASI, IGA, and SCORAD (extent of disease and disease severity) should be performed by the investigator. Efforts should be made that the same assessor performs the assessments of a particular participant throughout the study.
11. Participants will complete a worst itch and sleep quality NRS questionnaire with a 7-day period recall immediately prior to the visit day, and questionnaires for PGIS of AD and PGIC of AD. Participants should be reminded to answer all the questions.
12. Participants will complete the DLQI questionnaire to measure how much his/her skin problem has affected his/her life over the last week. Participants should be reminded to answer all the questions.
13. Participants who discontinue study treatment early (before completing the 4-week dosing period) should continue with all the remaining study visits. Participants who withdraw from the study any time before the Week 12 visit should complete the Week 12 (Day 85)/EOT visit at withdrawal. Participants who withdraw from study early after Week 12 should complete the Week 24 (Day 169)/EOS visit at withdrawal.

Abbreviations: AD = atopic dermatitis; ADA = anti-drug antibody; AE = adverse event; BMI = body mass index; CRP = C-reactive protein; DLQI = dermatology life quality index; EASI = eczema area and severity index; ECG = electrocardiogram; EOI = end of infusion; EOS = end of study; EOT = end of treatment; HBcAb = antibody to hepatitis B core antibody; HBsAb = hepatitis B surface antibody; HBsAg = hepatitis B surface antigen; hCG = human chorionic gonadotropin; HCV = hepatitis C virus; HIV = human immunodeficiency virus; IGA = investigator's global assessment; IV = intravenous; NRS = numerical rating scale; PGIC = patient global impression of change in AD; PGIS = patient global impression of severity of AD; PK = pharmacokinetic; S = serum; SCORAD = scoring atopic dermatitis; TARC = thymus- and activation-regulated chemokine; TB = tuberculosis; U = urine; V = visit; WCBP = women of childbearing potential

12.2 Partial Date Conventions

Algorithms for Adverse Events, Medical History, and Prior and Concomitant Medications

Partial date to be imputed as:

Start Date	Stop Date	Action
Complete	Complete	No action
Partial, but known components shows it can't be on or after study medication start	Complete	Impute the start date as "01", if only the day is missing. Impute the start date as "01 January", if month and day are missing.
	Date and/or month missing	Impute the stop date as the latest possible date (i.e., last day of the month, if only the day is missing or "31 December" if month and day are missing).
Partial, could be on or after the study medication start Or missing	Complete	
1) If stop date < study medication start then, Impute the start date as earliest possible date (i.e., "01", if only the day is missing or "01 January", if month and day are missing).2) If stop date \geq study medication start then, impute the start date equal to the study medication start date.
	Partial	Impute the stop date as the latest possible date (i.e., last day of the month, if only the day is missing or "31 December" if month and day are missing). then, 
1) If stop date < study medication start then, impute earliest possible date.2) If stop date \geq study medication start, then impute the start date equal to the study medication start date.
	Missing	Missing date will not be imputed.

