Participants who withdraw from the study any time before the Week 12 visit should complete the Week 12 (Day 85)/EOT visit at withdrawal.

Participants who withdraw from the study early after Week 12 should complete the Week 24 (Day 169)/EOS visit at withdrawal.

The study enrolled a total of 13 participants into Cohort 1 between July 18, 2023, and January 31, 2024. On March 18, 2024, the sponsor decided to terminate further screening and enrollment of patients into the study. The decision was made because of slower than expected enrollment and the expectation that data from Cohort 1, despite being a small open-label cohort, will provide valuable

information to inform the design of a more robust Phase 2b study. No safety concerns were noted. Therefore, the design and description related to Cohort 2 in this protocol is no longer applicable.

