Treatment-emergent AEs (TEAEs) are AEs that developed or worsened in severity compared to the baseline during the treatment and follow-up period. As only the worsening pre-existing AEs and new AEs reported during the treatment and follow-up period will be collected in the study, all AEs collected during the treatment and follow-up period are considered as TEAEs.

TEAE that are infusion related reaction will be summarized. These TEAEs are localized injection/infusion reactions that may include pruritus, pain, erythema, swelling, rashes, or bleeding around the injection/infusion site. Systemic injection/infusion-related reactions may be immediate type or delayed type immune complex-associated hypersensitivity reactions (e.g., serum sickness).

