6.3 Prior and Concomitant Medications/Procedures for AD

Below summaries will be provided on prior and concomitant medications/procedures for treatment of AD for the safety analysis set, sorted by decreasing frequency of anatomic therapeutic class (ATC) level 2 (pharmacological or therapeutic subgroup) and preferred term.

- Summary of prior medications related to AD by ATC level 2 and preferred term.
- Summary of prior medications related to AD by type of medication

- Summary of prior medications related to AD by reason for discontinuation, ATC level 2 and preferred term
- Summary of prior medications related to AD by reason for discontinuation and type of medication.
- Summary of concomitant medications related to AD by ATC level 2 and preferred term.
- Summary of rescue medication (RM) by ATC level 2 and preferred term
- Summary of the duration of RM by ATC level 2 and preferred term

The duration of RM will be calculated as:

$$(\text{Date of last usage of RM} - \text{Date of first usage of RM}) + 1$$

If a participant has utilized RM on multiple occasions, the total duration will be calculated as the cumulative sum of each RM duration. A summary of the duration of rescue medications by type of medication will be presented.

Listings will be provided for prior and concomitant medications/procedures for AD and rescue medication for the safety analysis set. The listings will include ATC level 2 and preferred terms, indication, dose, frequency, route, start date, study day onset (for medications started before treatment, the study day onset (defined as date of medication start - date of the first dose; for medications started on or after treatment, the study day onset = date of medication start - date of the first dose+1), the study end date (defined similarly as for study onset day)).

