6.9.1 Analysis of Adverse Events

Incidence tables for both non-TEAEs and TEAEs will be presented. The table will include the number (n) and percentage (%) of participants who are experiencing an adverse event, along with the corresponding number of episodes of AEs. Participants with multiple adverse events in a particular category will be counted only once in that category. Participants with multiple severities/grading will be counted only once under maximum severity/grading.

The number and proportion of participants reporting non-TEAEs/TEAEs will be summarized, sorted by decreasing frequency of SOC and PT, and in case of further ties, then alphabetically.

Listings will be provided by SOC and PT, for non-TEAEs, TEAEs and TESAEs, TEAEs of infusion related reactions, and TEAEs leading to study treatment discontinuation.

The following summaries will be provided for the adverse events.

- Overall summary of AEs: The overall summary of AEs will be provided with number and proportions of participants with any:
 - non-TEAE
 - TEAE
 - Related TEAE
 - SAE
 - TEAE by CTCAE grades
 - TEAE that are infusion related reaction
 - TEAE leading to 4-week dosing period discontinuation
 - TEAE leading to 12-week dosing period discontinuation
 - TEAE leading to study discontinuation
 - TEAE with outcome of death
- Summary of non-TEAEs by SOC and PT
- Summary of TEAEs by SOC and PT
- Summary of TEAE occurred during treatment period by SOC and PT
- Summary of TEAEs occurring for at least 2 participants by PT
- Summary of Serious TEAEs by SOC and PT
- Summary of TEAEs by PT and worst CTCAE grade
- Summary of TEAEs with CTCAE grade 3 or higher by PT
- Summary of treatment related TEAEs by SOC and PT

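### SAP 12.2 has no row for a partial start date known to fall after first dose; read plainly, it moves such records to Day 1 against their own recorded month or year

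*SAP*

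**What the plan says.** The table in SAP 12.2 covers adverse events, medical history, and prior and concomitant medications. An incomplete start date has two possible classes:

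- the known parts show that it cannot be on or after first dose; or
- "Partial, could be on or after the study medication start", a class that also takes wholly missing starts.

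In the second class, if the stop date is complete and on or after first dose, the rule is to "impute the start date equal to the study medication start date". If the stop is partial, it is first set to its latest possible date and the same rule then applies. If the stop is missing, the table says only "Missing date will not be imputed".

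SAP 7.2 refers back to this table and adds: "Imputed dates will not be presented in the listings". The only other partial-date rule, in SAP 4.1, is for the date of atopic dermatitis diagnosis.

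Outputs that can use these dates:

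- SAP 6.9.1: "Summary of TEAE occurred during treatment period by SOC and PT".
- SAP 6.3: rescue-medication duration, computed as last use minus first use plus one day. For repeated use, "the total duration will be calculated as the cumulative sum of each RM duration".
- Protocol 11.3.1, which includes TEAE duration among the safety variables to be summarized. SAP 6.9.1 has no such summary.

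**The concern.** A partial start is known to fall after first dose only when its recorded month or year is later than that of first dose. Setting it to first dose therefore always contradicts the record. The usual reason for imputing first dose is to count an event as treatment-emergent when its order relative to dosing is unknown. Here the order is known, so that reason does not apply.

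Three things can go wrong:

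- A follow-up event can be counted in the treatment-period TEAE table.
- Rescue duration, and any event duration that is reported, is overstated. With 13 participants, one such record can dominate a summary.
- A listing would show the date as recorded, so a reader cannot see from it which date a summary used.

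A fourth effect is conditional. The SAP text on rescue handling is redacted. The protocol synopsis makes a participant a non-responder from the time of high-potency corticosteroid or systemic rescue. If dates imputed under 12.2 feed that rule, visits before the true rescue would wrongly become non-response.

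**Working it through.** **Inputs.** The classes and actions are from SAP 12.2. SAP 2.3 puts the treatment period at Days 1 to 85 and follow-up at Days 86 to 169. Protocol 4.1 gives the enrolment range: "The study enrolled a total of 13 participants into Cohort 1 between July 18, 2023, and January 31, 2024". Assumption: first dose on the enrolment date. Study day = date − first-dose date + 1. Duration = stop − start + 1.

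**Example 1.** First dose 6 Nov 2023 (Day 1), start recorded as Mar 2024 with the day missing, stop 20 Mar 2024.

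- 1 Mar 2024 is Day 117 and 20 Mar is Day 136.
- As written: start Day 1, duration 136 − 1 + 1 = 136 days.
- Consistent with the record: start between Day 117 and Day 136, duration between 1 day and 136 − 117 + 1 = 20 days.

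**Example 2.** Same start; stop also recorded as Mar 2024 with the day missing, so set to 31 Mar (Day 147).

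- As written: 147 − 1 + 1 = 147 days.
- Consistent with the record: at most 147 − 117 + 1 = 31 days.

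**How often a post-dose start would fall in the gap if only its day is missing.** I took each of the 198 possible first-dose dates from 18 Jul 2023 to 31 Jan 2024.

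| Share of days | Minimum | Maximum | Mean |
|---|---|---|---|
| Days 2–169 in a calendar month after the first-dose month | 138/168 = 82% | 168/168 = 100% | 92% |
| Days 86–169 in a month that begins after Day 85 | 54/84 = 64% | 84/84 = 100% | 83% |

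For the example participant the shares are 144/168 = 86% and 82/84 = 98%. These describe the calendar, given that a partial date exists. They do not estimate how many such records there are.

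**Behaviour of the rule.** I applied it to every first-dose date in the range and every true onset from Day 1 to Day 169, with the day missing or the day and month missing, and a stop on Day 169. This gives 198 × 169 × 2 = 66,924 cases.

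- In 44,638 cases the recorded parts place the start after first dose. All 44,638 are dated to Day 1, outside the recorded month or year.
- In the other 66,924 − 44,638 = 22,286 cases, none of the imputed dates conflicts with the recorded parts.
- In 17,314 cases the earliest date consistent with the record is after Day 85. All 17,314 move into the treatment period.
- In all 44,638, the start is on or after first dose under both the present rule and a corrected one, so TEAE status is the same.

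**Conditional responder effect, example 1.** Weeks 1, 2, 4, 6, 8, 12 and 16 precede Day 117 (latest Week 16 visit: Day 113 + 3 = 116), which is seven visits. One participant is 1/13 = 7.7 percentage points at each of those visits where that participant would otherwise have responded. Week 20 is unaffected if held within ±3 days (earliest Day 141 − 3 = 138, after Day 136). The SAP 12.6 analysis window for Week 20 is wider (Days 121–148), so an out-of-window assessment could also be affected. Week 24 is not.

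**The case against.** The strongest points on the other side are these.

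- **Importance.** This is a single-arm, descriptive study of 13 participants, and the primary endpoint is untouched because "all AEs collected during the treatment and follow-up period are considered as TEAEs". That stands, and it limits the weight of the point.
- **Frequency.** Event start and stop dates are collected for every adverse event, visits are one to four weeks apart, and source data are verified. Post-dose records with a missing day may be few or none. That stands; the calendar shares do not answer it.
- **Reading.** Set against the first class, the second could mean only starts whose order is uncertain. The defect is then an unstated case rather than a wrong date. The rule would still be missing for most day-missing post-dose starts, so the table needs the same repair.
- **Outputs.** SAP 6.9.1 does not say that the treatment-period table uses imputed onset, and its summaries do not include event duration. That stands. Rescue duration remains as an output computed directly from the dates.
- **Responder effect.** It depends on redacted text and on several conditions holding together. That stands, so it is offered only as a conditional effect.
- **Listings.** They would still show the recorded month. That is fair; what they hide is the date used in the summaries.
- **Extraction.** The table was read from PDF, so a lost row cannot be fully excluded. The rows that bear on this point are coherent and show no gap or redaction.

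**Conclusion.** The concern holds. On the plain reading, SAP 12.2 gives a start date that the record itself contradicts whenever the recorded month or year is later than first dose and a stop date is recorded, complete or partial. On the narrower reading, those records have no rule.

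The size per record can be large: 136 days against at most 20, and 147 against at most 31, in the two examples. Rescue duration is affected directly, and the treatment-period TEAE table is affected if events are assigned by imputed onset. The responder effect is possible but cannot be confirmed from the public text. Total TEAE counts, and so the primary endpoint, do not change.

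The examples use an illustrative first-dose date, and the calendar shares assume first dose on the enrolment date. The number of affected records is unknown. This should be corrected before database lock; it does not threaten the main conclusion of the study.

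**What to change.** Add one row to SAP 12.2: for a partial start whose known parts place it after first dose, impute the earliest date consistent with those parts, that is, the first of the known month, or 1 January if only the year is known. Restrict imputation to the first-dose date to starts that are wholly missing or whose known parts are compatible with it. If a recorded stop precedes the earliest possible start, the two dates conflict and should be queried rather than imputed around.

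Clarify the missing-stop row. For adverse events and on-study or rescue medications with a partial start and a missing or ongoing stop, apply the same start rule and leave the stop missing. Leave unimputed, as now, wholly missing starts with a missing stop, and ongoing medical history and prior medications.

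A year-only start remains imprecise. In the example, 2024 alone gives 1 Jan 2024, which is Day 57 and still in the treatment period, but it no longer contradicts the record.

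The cost is one added row, one clarified row and a small program change. Total TEAE counts stay the same; treatment-period counts and rescue durations may change, which is the purpose.
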